3.5. Sample size calculations

The sample sizes presented in Table 4 have been calculated using Stata 17© according to the following assumptions:

1. No pre-post correlations are assumed as there are no reliable sources of these for externalising behaviours and estimating them would add uncertainty to the final

sample size calculation. By omitting this parameter, we obtain a conservative estimate of sample size for an analysis of covariance.

2. The adolescent population SDQ (externalising scale) mean is 6.0 and the assumed pooled Standard Deviation (SD) is 1.74⁸, using the UK self-report population norms for 11-15 year olds⁹. Thus, to detect an effect size of 0.2 or greater we need a SDQ externalising behaviours score difference of 6.0 (control) versus 5.66 (intervention). This difference requires 527 participants in each group, 1,054 for the whole sample.
3. Assuming 10% pupil-level attrition between baseline and follow-up requires a total sample size of 1,172.
4. Following Shackleton, Hale, Bonell, and Viner (2016) and Parker, Nunns, Xiao, Ford, and Ukoumunne (2021), with an ICC of 0.03 and a harmonic mean year group of 200 pupils, based on the average year group size in England of 197 (ONS, 2023) of whom 80%, 160, will consent to participate, the design effect is 5.8 (1+(0.03*160)), which inflates the sample to 6,798 (5.8*1,172).
5. Given assumptions 1 to 4 above, we need a minimum of at least 25 schools in each arm for an efficient cluster trial, that is 50 schools in total. Nevertheless, we propose double the sample size aiming to recruit 100 schools with 50 on each arm. The rationale for this is further discussed below. Table 2 provides an overview of the numbers available at the primary endpoint for a variety of school retention rates (100%, 90%, 80%, 70%, 60%) and pupil retention rates (100%, 90%, 80%, 70% and 60%) scenarios. In all scenarios the numbers recruited and followed up are sufficient to meet the sample size requirements when we account for the different design effects (i.e., as more pupils drop out, the design effect, which is a function of the cluster size, decreases, hence the overall sample size decreases).

Table 2 Impact of different pupil and school retention rates on sample size

		Proportion of pupils retained				
		100%	90%	80%	70%	60%
Number of schools retained	100	16,000	14,400	12,800	11,200	9,600

⁸ The SD has been estimated as the standardised SD using the same raw data for both scales

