⁹ <https://www.sdqinfo.org/norms/UKNorm1.pdf>

	90	14,400	12,800	11,200	9,600	8,640
	80	12,800	11,200	9,600	8,640	7,680
	70	11,200	9,600	8,640	7,860	6,720
	60	9,600	8,640	7,860	6,720	5,760

Table 3 Impact of different pupil and school retention rates on MDES

		Proportion of pupils retained				
		100%	90%	80%	70%	60%
Number of schools retained	100	0.1064	0.1074	0.1086	0.1102	0.1122
	90	0.1122	0.1132	0.1145	0.1161	0.1183
	80	0.1190	0.1201	0.1214	0.1232	0.1255
	70	0.1272	0.1284	0.1298	0.1317	0.1341
	60	0.1374	0.1385	0.1402	0.1422	0.1449

Several considerations come into play to target 100 schools and 16,000 young people. First, a larger pool of schools increases the likelihood of recruiting a diverse population of school types (e.g., school-level of deprivation, FSM, different socioeconomic backgrounds) and student demographics, enabling robust subgroup analyses and generalizability of findings across various contexts. Second, a large overall sample size enhances statistical power to detect smaller but potentially meaningful intervention effects, minimising the risk of false negatives and providing reliable findings to inform future interventions. Third, the target sample size was selected to ensure sufficient power for the quasi-experimental design (QED) analysis focused on a targeted subgroup of students. Lastly, a larger sample size accommodates the cluster randomised trial design, accounting for potential clustering effects and maintaining adequate power for the primary analysis.

The sample size calculation has also considered **the trade-off between internal/external validity and ethical considerations**. Thus, outcomes will be measured on a specific cohort rather than the whole school population to minimise the burden on schools, school staff, and students while achieving efficient data collection. Through co-production workshops with teachers and a youth advisory board, the Year 8 cohort (2023/2024) was carefully selected as the appropriate group for measurement.

Table 4 Sample size calculations

		Scenario 1
Minimum Detectable Effect Size (MDES)		0.1064
Pre-test/ post-test correlations	level 1 (participant)	n/a
	level 2 (cluster)	n/a
Intracluster correlations (ICCs)	level 1 (participant)	n/a
	level 2 (cluster)	0.03
Alpha		0.05
Power		0.8
One-sided or two-sided?		2
Average cluster size (if clustered)		160¹⁰
Number of clusters	Intervention	50
	Control	50
	Total	100

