	70	0.1272	0.1284	0.1298	0.1317	0.1341
	60	0.1374	0.1385	0.1402	0.1422	0.1449

Rationale for Targeting 100 Schools

Targeting 100 schools and 16,000 students is justified by several considerations. First, a larger pool of schools increases the likelihood of recruiting a diverse population of school types (e.g., school-level of deprivation, FSM, different socioeconomic backgrounds) and student demographics, enabling robust subgroup analyses and generalizability of findings across various contexts. Second, a large overall sample size enhances statistical power to detect smaller but potentially meaningful intervention effects, minimising the risk of false negatives and providing reliable findings to inform future interventions. Third, the target sample size was selected to ensure sufficient power for the quasi-experimental design (QED) analysis focused on a targeted subgroup of students. Lastly, a larger sample size accommodates the cluster randomised trial design, accounting for potential clustering effects and maintaining adequate power for the primary analysis.

Table 4 displays the minimum detectable effect in the protocol according to the assumed parameters, target sample size, and the respective effect size after randomisation driven by the achieved number of responses on the primary outcome. Thus, while the MDES in the protocol is an estimation from the assumptions, the MDES estimated in the column 'Randomisation' corresponds to the actual achieved sample size at baseline in the primary outcome from the schools that were randomised. As we are adopting an intention-to-treat approach, the estimation includes responses from 4 schools that dropped out after randomisation.⁵ Those four schools that dropped out belong to the intervention group.

⁵ This means that now the number of schools in the trial are 74 with 4 dropping out from the intervention group after randomisation

Table 4 Sample size calculations and effects size

		Protocol	Randomisation
Minimum Detectable Effect Size (MDES)		0.1064	0.094
Pre-test/ post-test correlations	level 1 (participant)	n/a	n/a
	level 2 (cluster)	n/a	n/a
Intracluster correlations (ICCs)	level 1 (participant)	n/a	n/a
	level 2 (cluster)	0.03	0.015
Alpha		0.05	0.05
Power		0.8	0.8
One-sided or two-sided?		Two-sided	Two-sided
Average cluster size		160⁶	166⁷
Number of clusters	intervention	50	40
	control	50	38
	Total	100	78 ⁸

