⁶ Average school size in England is 986, average year size is 200 and accounting for a potential 20% not consenting, hence, cluster size 160.

⁷ This is the actual cluster average size

⁸ Although the initial plan was to allocate schools equally to the intervention and control groups at the randomisation stage, the achieved sample showed a slight difference due to attrition during the recruitment

		Protocol	Randomisation
Number of participants	intervention	8,000	6,391
	control	8,000	7,214
	Total	16,000	13,393 ⁹

The MDES calculations were performed using PowerUp! Tool, developed by Dong and Maynard (2013), which incorporates the formula below according to Bloom, Richburg-Hayes, and Black (2007), for the two-level cluster randomised controlled trials:

$$MDES = M_{n-k*-2} \sqrt{\left(\frac{\rho(1 - R_C^2)}{P(1 - P)J}\right) + \left(\frac{(1 - \rho)(1 - R_i^2)}{P(1 - P)Jm}\right)}$$

Employing this formula enables the inclusion of baseline covariates at the cluster (school) level, pupil level, or both. Our analysis strategy intends to use mean-centered baseline scores within the multilevel models at both the pupil and school levels. Incorporating a covariate at both levels - school and pupil - enhances the trial's precision, resulting in a reduced Minimum Detectable Effect Size (MDES) estimate compared to methodologies that employ only one covariate or none.

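### The planned MDES of 0.1064 and all of Table 3 rest on a normal multiplier, not the degrees-of-freedom multiplier in the SAP's formula, and the headline takes the no-loss cell although 10% pupil attrition is planned

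*Protocol*

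**What the plan says.** Protocol section 3.5 plans for pupil loss in assumption 3: "Assuming 10% pupil-level attrition between baseline and follow-up requires a total sample size of 1,172". Assumption 4 proceeds "with an ICC of 0.03 and a harmonic mean year group of 200 pupils" and takes 80% consent, which gives 160 per school. The footnote to Table 4 derives 160 the same way, from 20% non-consent alone.

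The grid headed "Table 3 Impact of different pupil and school retention rates on MDES" has the first row "100 0.1064 0.1074 0.1086 0.1102 0.1122", which runs from 100% down to 60% of pupils retained at 100 schools. Table 4 then states "Minimum Detectable Effect Size (MDES) 0.1064", with alpha 0.05 two-sided, power 0.8, ICC 0.03, 50 schools per arm and 16,000 pupils. SAP section 2.2 repeats both tables.

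On method, the Protocol prints no MDES formula and names Stata 17 for the sample sizes in Table 4. SAP section 2.2 also names Stata 17, but later in the section says "The MDES calculations were performed using PowerUp! Tool". It then prints the two-level cluster formula with a multiplier M subscripted n − k* − 2. SAP Table 4 adds a Randomisation column with an MDES of 0.094, which the text says "corresponds to the actual achieved sample size at baseline in the primary outcome from the schools that were randomised".

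On attrition, a footnote in SAP section 2.3.8 explains a 20% loss as 10% attrition plus 10% non-consent.

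**The concern.** A multiplier indexed by degrees of freedom is a t multiplier; a normal multiplier has none. Treatment is allocated to schools, so the relevant degrees of freedom come from the number of schools. Using the normal value always makes the MDES look smaller. The shortfall grows as schools are lost, which is the situation the lower rows of Table 3 are meant to describe.

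Separately, the headline describes a sample that the same section does not expect to have at the primary endpoint.

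The MDES is the trial's power statement to its funder, whose requirement is a value below 0.20. Printed values that cannot be recovered from the printed formula, and that err on the favourable side, weaken that statement even if the error is small.

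**Working it through.** **Inputs.** ICC ρ = 0.03, P = 0.5, J = 100 schools, two-sided alpha 0.05 and power 0.8 (Protocol Table 4). No pre/post correlation, so both R² terms are 0 (assumption 1). Cluster size m = 160 × proportion of pupils retained. The formula is the one printed in SAP section 2.2:

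MDES = M × √[ρ/(P(1−P)J) + (1−ρ)/(P(1−P)Jm)]

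**1. Reproduce the headline.** With J = 100 and m = 160, the root is √(0.03/25 + 0.97/4,000) = √(0.0012 + 0.0002425) = 0.03798.
- Normal multiplier: z(0.975) + z(0.80) = 2.8016, and 2.8016 × 0.03798 = 0.1064, the stated figure.
- t multiplier on J − 2 = 98 df: 2.8298 × 0.03798 = 0.1075.

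**2. Check the whole of Table 3.** The normal multiplier matches 24 of 25 cells to four decimals. The exception is 60 schools with 90% of pupils, printed as 0.1385 where the normal multiplier gives 0.13865 (0.1387 rounded). That is a last-digit slip, not a t value, since t gives 0.1410. The t multiplier on J − 2 or J − 3 df matches no cell, and nor does the exact noncentral t. The cruder design effect 1 + 0.03m, which the documents use for the minimum sample, gives 0.1067 in the first cell, so it is not the source either.

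| Schools | Pupils retained | Stated | Normal | t, J − 2 df |
|---|---|---|---|---|
| 100 | 100% | 0.1064 | 0.1064 | 0.1075 |
| 100 | 90% | 0.1074 | 0.1074 | 0.1085 |
| 80 | 80% | 0.1214 | 0.1214 | 0.1230 |
| 60 | 90% | 0.1385 | 0.1387 | 0.1410 |
| 60 | 60% | 0.1449 | 0.1449 | 0.1473 |

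Every stated value is below its t value, by 0.0011 to 0.0025. The ratio of multipliers is 2.8298/2.8016 = 1.010 at 100 schools and 2.8496/2.8016 = 1.017 at 60. The largest rise, 1.8%, occurs in the cell with the slip.

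**3. Apply the planned attrition.** At 10% pupil loss m = 144, and the root is √(0.0012 + 0.97/3,600) = 0.03833. The normal multiplier gives 0.1074, already printed in Table 3; t gives 0.1085. Against the headline, 0.1085/0.1064 = 1.020.

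**4. Power at an effect of 0.1064 with the t test.** 79.2% with no loss and 78.5% with 10% loss, against 80% stated.

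**5. The Randomisation column.** With 78 schools (40/38), m = 166 and ICC 0.015, t gives 0.0930 and normal 0.0918. The stated 0.094 is above both.

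**The case against.** **Which tool produced the figures.** The Protocol prints no formula, and both documents also name Stata 17. It would go too far to say that the Protocol misapplied its own formula. What stands is that the SAP attributes its MDES calculations to PowerUp! and the printed formula, exempts no column, and then shows values that do not follow from it.

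**Whether the subscript means t.** The SAP never writes t and does not define the n in the subscript. If n counted pupils (16,000 − 2 = 15,998), the multiplier would be practically the normal one. That reading does not suit a design in which treatment varies only between schools, but it is a reason to state the multiplier outright.

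**Attrition is disclosed.** A reader might infer that attrition was ignored. It was not: the 1,172 in assumption 3 includes it and is carried into the 6,798, and Table 3 prints the 90% case and heavier losses. Only the choice of headline cell is at issue. The SAP's split of the 20% would also make 160 already net of attrition. That conflicts with Protocol section 3.5 and with Table 3's label of 100% retained, and the documents do not resolve it.

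**The zero correlation is conservative.** This is true and works the other way. Since (0.1064/0.1085)² = 0.962, an R² of about 0.04 at both levels, a correlation of about 0.20, would cancel the full move to 0.1085. The figures are therefore too favourable on these two points, not necessarily for the baseline-adjusted analysis that is planned.

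**Conclusion.** The point holds as a small reporting error. Table 3 and the Protocol MDES of 0.1064 use the normal multiplier, while the formula given as their source carries a degrees-of-freedom multiplier. Correcting this raises each cell by 1.0% to 1.8%. The headline becomes 0.1075 with no loss and 0.1085 at the planned 10% pupil attrition. This rests on school-based degrees of freedom, ρ = 0.03, zero correlation, and 160 being the number before attrition. If 160 is already net of attrition, the headline is 0.1075.

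Two stronger readings are not supported:
- **That the trial is underpowered.** The largest corrected value in Table 3 is 0.1473, well below 0.20, and power at 0.1064 falls by at most 1.5 points.
- **That the Randomisation figure of 0.094 is too favourable in the same way.** It is openly labelled as a baseline figure that keeps the four departed schools under intention to treat. It is slightly less favourable than the t formula gives at its own inputs (0.0930).

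**What to change.** - Recompute Table 3 and the Protocol column of Table 4, in both documents, with the t multiplier on J − 2 df (or J − k − 2 with k school-level covariates). Correct the slip at 60 schools and 90% of pupils at the same time.
- State which tool produced the MDES figures, Stata 17 or PowerUp!, and define the subscript of M.
- Reconcile the 20% non-consent in Protocol section 3.5 with the 10% attrition plus 10% non-consent in SAP section 2.3.8. Then quote the headline at planned attrition: 0.1085 if 160 is before attrition, 0.1075 if it is already net.
- Leave 0.094 labelled as a baseline figure. A follow-up figure may be added beside it as a stated scenario. With 74 schools (36/38), m = 166 × 0.9 = 149.4 and ICC 0.015 it is about 0.097. First reconcile the average cluster size, since 166 is printed but 13,393/78 = 171.7.

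The cost is edits to two tables and a few sentences. The headline becomes 1% to 2% less favourable, with no change to design, enrolment or analysis.

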4.1. Analysis

The analysis will be conducted using an analysis by intention to treat (ITT) and will include all available data maintaining participants as members of their allocated group. The primary analysis will likely take the form of a linear regression model, adjusted for baseline stratification covariates (above/below the median proportion of FSM6) and the baseline value of the outcome. As there is variation across sites, a multi-level model will be applied, considering pupils are nested within schools (random effect).

As discussed in section 3.3 the minimisation method incorporates %FSM6 as a stratifying factor, ensuring that schools with similar levels of FSM6 are evenly distributed across the control and intervention conditions. After baseline testing, the evaluation team will check balances across arms. If, by chance, randomisation had not achieved the desired balance on those key socio-demographic characteristics that may affect outcomes, we may consider a multilevel analysis of covariance (ML-ANCOVA) as an additional model to test the robustness of our results. Nevertheless, if the randomisation incorporates % of FSM, it is unlikely that there is an imbalance across arms on FSM.

Secondary outcomes will be assessed similarly by establishing diagnostic plots to identify the most appropriate regression approach, including stratification factors and baseline covariates within a multi-level model. Diagnostic plots are graphical tools used to assess the assumptions and fit of a statistical model. These may include residual plots (e.g., residuals vs. fitted values, normal Q-Q plots) to check for non-linear patterns, unequal variance, outliers, and normality assumptions. Partial regression plots can be used to examine the relationship between the outcome and specific predictors, while leverage plots help identify influential observations. Additionally, added variable plots can assess the linearity assumption between the outcome and predictors. Outcomes at individual level (CYP and school staff) will be approached through multi-level analysis, while outcomes at the school level will be done through linear regression.

Stepwise regression analysis will be performed to model the relationship between pre-randomisation factors and demographics on observed outcomes at 15 months. Interaction terms with the allocation arm will be included in the analysis, and a significance level of 0.1 will be used to determine which factors are to be included in the regression model. Pre-

randomisation factors will include pupil sex, FSM status and ethnicity. This analysis will be augmented by an additional analysis including participants in the intervention arm using the same pre-randomisation factors, process measures of intervention delivery, and staff changes in perceptions of trauma-informed care.

Table 6 sets out the statistical analysis for each outcome by level.

Table 6 Statistical analysis by outcome and level

Outcome	Level	Model	Covariates
Primary outcome Externalising behaviour Secondary outcomes Internalising behaviour Non-psychotic psychological distress Well-being Sense of connectedness Exclusions, suspensions and attendance at individual (CYP) level	CYP	Multi-level model	Pre-treatment scores of outcomes at CYP level Demographic factors (sex, FSM status) at CYP level
Secondary outcomes Attitudes related to TIC Well-being	School staff	Multi-level model	Pre-treatment scores of outcomes at staff level
Secondary outcomes Staff retention Staff sickness Exclusions & suspensions of CYP School attendance of CYP	School	Linear regression (OLS)	Pre-treatment scores of outcomes at school level

Sub-group analysis

The sub-group analysis will be twofold. First, we will conduct a latent class analysis (LCA) on the intervention group to explore whether there are emerging sub-groups with differential effects. LCA refers to the model whose underlying indicators are all categorical while for the continuous case, LCA is known as latent profile analysis (LPA) (Sinha, Calfee, & Delucchi, 2021). The LCA model will include the socio-demographic variables (sex, ethnicity, FSM) together with primary and secondary outcomes. This will allow us to observe 'latent' groups emerging from the data.

Second, we will conduct multilevel model by sub-groups considering a model with interaction may be more demanding in terms of power analysis. However, we will also consider for robustness check a multilevel model with interaction between treatment and sub-group dummy variable.

Missing data

We do not anticipate large amounts of missing data. If the missing data exceeds 5%, sensitivity analyses will be performed using a pattern mixture approach and multiple imputations will be conducted to compare the sensitivity of conclusions to varying assumptions about the missing data, notably whether data are missing at random (MAR) or missing not at random (MNAR) to allow for an assessment of both random and systemic bias. The variation of the primary outcome by different assumptions of missing data will be presented.

Compliance

We will conduct a Complier Average Causal Effects (CACE) analysis using an instrumental variable framework to explore the impact of compliance on the primary outcomes at different levels of compliance. CACE weighs the intention-to-treat (ITT) treatment effect by the proportion of compliance, this allows the estimation of unbiased treatment effects and maintains the allocation in the analysis. The CACE analysis will be implemented using a two-stage least squares (2SLS) approach clustering the standard errors, where the first stage models compliance as a function of the randomised treatment assignment, and the second stage models the outcome as a function of the predicted compliance from the first stage and other covariates.

Compliance will be measured at the school level through a binary variable, compliance (Yes/No). Compliance for those schools in the intervention arm will be assessed based on the level of engagement. Section 5 discusses an engagement tool in more detail. The engagement tool assesses level of schools engagement with the delivery of TISUK intervention across five key dimensions:

- Individual Training,
- Whole Staff Training,
- Consultancy,
- Reflective Supervision,
- Webinars.

Each dimension is scored based on specific criteria, such as the number of staff trained, attendance at meetings, and utilisation of resources. The tool uses a point-based system, with 100 points possible across all dimensions. The final score is calculated as a percentage, with clear thresholds for interpretation:

- up to 50% indicates poor engagement,
- 51-75% moderate engagement,
- 76-90% good engagement, and
- 90-100% excellent engagement.

The score will be used to measure compliance in the CACE analysis. CACE weighs the intention-to-treat (ITT) treatment effect by the proportion of compliance, allowing for the estimation of unbiased treatment effects while maintaining the original randomisation in the analysis. Therefore, a school in the intervention arm will be considered compliant with the trial if showing engagement of 76% or higher. As a robustness check in the analysis, we will explore how compliance is associated with the outcomes and if any threshold for minimum compliance emerges by setting compliance at 76%, 80% and 90% of the engagement tool. This finding could serve in the future of a trial to establish a minimum threshold that ensures a successful delivery.

Quasi-experimental design on targeted intervention

Appendix 2 provides more details on the QED research design and analysis, including research questions and sample size analysis. To explore the impact of the intervention on a targeted group of CYP who are receiving tailored support, we will undertake a study within a trial (SWAT).

A full statistical analysis plan would be developed during the project, and we are committed to working with the approaches set out within the YEF's analysis guidance.

5. Implementation and process evaluation (IPE)

Following the process evaluation guidelines recommended by the EEF (Humphrey et al., 2016), we aim to conduct a process evaluation that delves into the intricate aspects of TISUK. This intervention, designed to promote a trauma-informed approach by fostering changes in policies and practices across the entire school, requires testing moderators and assumptions that link the pathways from inputs and activities to outcomes at CYP, school staff and school levels.

The main focus of the process evaluation will be to accurately assess the extent to which the intervention is implemented as intended throughout the school, ensuring fidelity to the intervention's principles. In addition to fidelity, other dimensions to test are: dosage, responsiveness, quality, and reach.

